2. DOCUMENT HISTORY

Version	Protocol version issue date	Short description of modifications
1	04/08/2020	Original Protocol (Version 1)
2	23/02/2021	Adapted protocol (Version 2)

3. SYNOPSIS

STUDY TITLE	A randomized controlled, single centre, study evaluating the impact of Virtual Reality Hypnosis during labor										
SHORT TITLE	VRH4L (Hypnotic Virtual Reality for Labor pain relief)										
PROTOCOL NUMBER	2										
SPONSOR	Department of Anesthesia, Clinique Saint-Jean Bruxelles (SJ)										
STUDY POPULATION	Women during labor										
PHASE	Prospective interventional Randomized Controlled Trial (RCT)										
STUDY DESIGN	
This prospective interventional RCT will evaluate efficacy of Virtual Reality Hypnosis (VRH) in reducing pain during labor. Hypnosis is delivered as a standardized therapeutic intervention through virtual reality, using a digital sedation software. This VRH module is called AQUA[©] (Oncomfort SA) and is specifically designed for the management of pain and anxiety during labor.
 
Women who are planning to give birth at the St-Jean Hospital are recruited at prenatal consultation some weeks before the calculated delivery date. Only patients with a planned induced labor can be included. Patients who agree to participate sign an informed consent form.
 
38 patients will be randomized in two arms (19 patients in each cohort):
 
 Patients in the intervention groups will receive a session of the AQUA[©] Digital Sedation module when in active labor (cervical dilatation ≥ 4 cm, contractions every 5 minutes, NRS pain score $\geq 4/10$) on top of the standard of care Patients in the control group will receive standard of care only. 
Patients are allowed to discontinue the VRH session at any time. A study staff member is present during the session to explain the intervention and fill in the questionnaires. Furthermore, she/he ensures the patient is receiving appropriate clinical care throughout the duration of the intervention.
 
Information from patient's report will be collected before the intervention, after the intervention and up to the patient's discharge from the maternity on day after childbirth. A log will be kept of patients who refuse to participate in the study.
										
OBJECTIVES AND ENDPOINTS	
 
 Primary objective	Primary endpoints	
 
 To evaluate efficacy of VRH AQUA[©] module on labor-related pain	Difference in NRS (Numerical Rating Scale 0 to 10) pain scores before and after the intervention	
 
 Secondary objectives	Secondary endpoints	
 
 To compare patient experience in both arms	 
Measure of NRS pain after 30 minutes
 
Measure of satisfaction by Likert Scale (0 to 5)
 
Measure of nausea by Nausea and Vomiting Score (0 to 3)
 
Evaluation of comfort during intervention with the CPOT scale (Critical care Patient Observation Tool 0 to 8) and heart rate
 
Willingness to undergo a potential next labor with VRH
 
Willingness to recommend VRH to acquaintances
 	
 
 To assess selected safety and efficacy outcomes in both arms	 
Progression of labor
 
Need for epidural
 	
 
	Primary objective	Primary endpoints	To evaluate efficacy of VRH AQUA [©] module on labor-related pain	Difference in NRS (Numerical Rating Scale 0 to 10) pain scores before and after the intervention	Secondary objectives	Secondary endpoints	To compare patient experience in both arms	
Measure of NRS pain after 30 minutes
 
Measure of satisfaction by Likert Scale (0 to 5)
 
Measure of nausea by Nausea and Vomiting Score (0 to 3)
 
Evaluation of comfort during intervention with the CPOT scale (Critical care Patient Observation Tool 0 to 8) and heart rate
 
Willingness to undergo a potential next labor with VRH
 
Willingness to recommend VRH to acquaintances
	To assess selected safety and efficacy outcomes in both arms	
Progression of labor
 
Need for epidural

Primary objective	Primary endpoints										
To evaluate efficacy of VRH AQUA [©] module on labor-related pain	Difference in NRS (Numerical Rating Scale 0 to 10) pain scores before and after the intervention										
Secondary objectives	Secondary endpoints										
To compare patient experience in both arms	
Measure of NRS pain after 30 minutes
 
Measure of satisfaction by Likert Scale (0 to 5)
 
Measure of nausea by Nausea and Vomiting Score (0 to 3)
 
Evaluation of comfort during intervention with the CPOT scale (Critical care Patient Observation Tool 0 to 8) and heart rate
 
Willingness to undergo a potential next labor with VRH
 
Willingness to recommend VRH to acquaintances
										
To assess selected safety and efficacy outcomes in both arms	
Progression of labor
 
Need for epidural
										

	
Need for medication: type and dosages during stay
 
Frequency and type of (severe) adverse events (SAEs) (mother and baby)
 
If the patient removes the headset during the session, motivation is documented.

	
To assess gynecologist and nurse satisfaction
 
Measure of satisfaction of the midwife and obstetrician by the Likert scale (0 to 5)
 
Quality of the therapeutic relationship between the midwife and patient (reported by the midwife in a NRS from 0 to 10)

	
Evaluation of vital signs
 
Oxygen saturation
 
Systolic and diastolic blood pressure
 
Heart rate (during and in between contractions)

NUMBERS OF PARTICIPANTS	38
INCLUSION CRITERIA	
 1. Age: ≥ 18 and ≤ 45 years 2. Pregnant with term gestation 3. Willing to adhere to the rules linked to the use of the VRH headset: turning off mobile phone, visit bathroom in advance, no new visitors and no interference of the partner other than when the woman would ask him so 4. Provision of written informed consent 5. Induced labor
EXCLUSION CRITERIA	
 1. Complicated pregnancy (HELLP,...) 2. Scheduled caesarian delivery 3. Receipt of epidural analgesia or opioid painkillers before start active labor phase 4. Low auditory acuity that precludes use of the device 5. Low visual acuity that precludes use of the device 6. Head or face wounds precluding use of the device 7. Schizophrenia 8. Epilepsy 9. Dizziness 10. Non-proficiency in French and/or Dutch (research language)
MEDICAL DEVICE	
The Digital Sedation session used is the AQUA[©] (module 3.2) delivered through the SedakitTM, both developed by Oncomfort®.
 
According to Annex IX of Directive 93/42 / EEC, the SedakitTM is classified as a Class I Medical Device, it is a non-invasive device that is in contact only with the skin. The SedakitTM consists of an audio headset, virtual reality goggles, a mobile phone, AQUA[©] software and the user's manual.
 
Digital Sedation allows an immersive experience of virtual reality focused on the induction of relaxation. As a solution for non-pharmacological sedation and self-management of pain and anxiety, AQUA[©] takes the subject into a deep sensory experience and allows her to dive into a soothing environment. The subject will be required to perform simple stress management exercises; helping her to better manage her pain and anxiety.
 
The techniques used is a virtual reality headset combined with an audio recording of psychological interventions, mainly clinical hypnosis.

STATISTICAL ASPECTS	Inclusion of 38 patients is necessary to ensure statistical significance. Participants are randomized and the investigators are not blinded.
STUDY MILESTONES	
First patient, first visit: March 1, 2021
 
Last patient, last visit: May 30, 2021

4. RATIONALE

4.1. CONTEXT AND JUSTIFICATION OF THE STUDY

Labor pain is feared by many women. However some women recall positive feelings about their coping ability with this intense pain. The way they dealt with pain seems more important than the severity of the labor pain. The feeling of being in control, respected and nurtured by caregivers and loved ones is what these women recall mostly.ⁱ

On the other hand, many women recall feelings of suffering, loneliness and helplessness. These negative feelings make the whole childbirth experience unpleasant. Even a posttraumatic stress disorder can develop after childbirth. The ability to cope with this pain is influenced by experiences that took place before childbirth. It is probably more likely to have dysfunctional coping skills when earlier traumas were never resolved.^j We believe that Virtual Reality Hypnosis (VRH) can improve the way women cope with pain during labor. Through self-hypnosis, the focus is moved from pain to positive feelings, thereby women feel less tensed and have a greater sense of self-control.

Secondly women are increasingly striving for a more natural birth, minimizing medical interventions such as cervical examination, pharmacological analgesia, etc. As such they are looking for nonpharmacological approaches to decrease labor pain.

There are different nonpharmacological (see section 4.1.2 alternatives for standard of care) techniques that can reduce side-effects, increase rates of breast feeding, and eventually increase satisfaction.^{ii,iii}

Immersive virtual reality (VR) has been shown to decrease pain in a non-pharmacological way and in a number of different situations.^{iv,v} Studies are positive about the use of immersive VR therapy as analgesia during experimental pain in healthy subjects, changing dressings of burn patients and as an analgesic adjunct during physiotherapy.^{vi vii viii}

The pain accompanied with childbirth is nor acute nor chronic and thereby a complex unique experience for every woman. Some studies suggest that VR can help controlling the pain during the active stage of labor. Outcomes like anxiety, use of pharmacological analgesia and satisfaction have also been studied.^{ix,x,xi}

Could the association of hypnosis with immersive VR have additive positive effects? Based on our internal experience, the use of Virtual Reality Hypnose (VRH) can increase the comfort for women in labor. We decided therefore to organize a trial to measure the benefits and side effects of this new technique. VRH has never been studied before as an analgesic for labor pain.

The hypnotic virtual reality environments are designed by Oncomfort SA, a Belgian company who's solution has already been extensively researched and published.^{xii} The VRH session is a module called AQUA©, a relaxing experience based on clinical hypnosis, respiratory techniques and autogenic muscle relaxation. This hypnotic script will bring the patient in a state of auto-hypnosis. The Head Mounted Display (HMD) is a VR Gear from Samsung-Oculus and the mobile phone used is a Samsung Galaxy S7.

4.1.1. Standard of care

The standard treatment (ST) for labor pain as used in our hospital contains massage, aquatherapy and postural exercises. This is always available for any woman in labor. The VR group receives digital sedation and when asked the ST. In comparison to the control group who receives only the ST when asked.

If ST is not sufficient, a patient can receive a pharmacological treatment or an epidural analgesia. However, in this study we will examine the efficacy of VRH before the use of epidural analgesia or pharmacological treatment.

4.1.2. Alternatives to standard of care

Audio-analgesia, aromatherapy, biofeedback, acupressure, TENS (Transcutaneous Electric Neurologic Stimulation) and massage are popular methods but are not proven to have a significant effect on labor pain. These are not available in our institution. On the other hand hydrotherapy, acupuncture and hypnosis have a proven significance as a tool for pain management during labor.^{xiii} More specifically hypnosis may reduce the overall use of analgesia during labor.^{xiv}

4.1.3. *Hypothesis*

Our primary goal is to evaluate the analgesic benefits of Virtual Reality Hypnosis (VRH) compared to the standard of care (ST) solely.

5. STUDY OBJECTIVES

5.1 PRIMARY OUTCOME

The primary endpoint is to compare the differences in NRS pain measured before and after the intervention during labor. (T3 minus T1) The Pain Numerical rating Scale (NRS) is a scale from 0 to 10 well known by the medical staff.^{xv xvi}

5.2 SECONDARY OUTCOMES

30 min after the end of the intervention the NRS pain is assessed once more. (T4)

During the intervention the comfort of the patient is evaluated. (T2) To do this we use the CPOT (Critical care Pain Observation Tool). CPOT is a comfort scale for (non)-ventilated patients in the intensive care unit. We decided to use this score, because during the VR experience we cannot communicate with the patient, which is similar as in sedated patients. And in our own experience we see that the parameters that we look at to evaluate the comfort of the patient during a VR sedation are very similar to this scale. (Facial expression, body movements, muscle tension and vocalization together make a score of 0 to 8)^{xvii} Vital signs like heart rate and blood pressure are parameters that are easily measured during the intervention and considered as objective for evaluating pain during labor. (T1,2,3,4) ^{xviii}

Nausea is also actively evaluated. Therefore we use the PONV rating scale from 0 to 3. (T1, T3, T4) Anxiety is evaluated with the NRS at the same time. (T1, T2, T3) We use the Likert satisfaction scale (from 0 to 5) to explore the satisfaction directly after their experience and the day after delivery. (T3, T6)

Willingness to repeat the intervention and to recommend the intervention can correlate with satisfaction of the overall experience. (T6)

Progression of labor is followed with the degree of the cervix dilatation, therefore we will not perform more cervical examinations than needed but interpret the measurement of the midwives/obstetricians. (T5)

The midwives are asked to evaluate the therapeutic link between themselves and the patient (NRS) after the women return to the maternity ward. (T5)

All the medication received during the stay on the delivery ward, adverse events and interruptions from the intervention is noted. (T3, T5)

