6. STUDY DESIGN

The VRH4L trial is an interventional, randomized, controlled, single-center, parallel group trial. Randomization will be done as a block randomization with a 1:1 allocation^{xix}

Clinique Saint-Jean Brussels (SJ), where the study takes place, is an academic hospital in the center of Brussels with around 2000 deliveries per year.

We create two groups: the VRH group and the control group. During the intervention (T1-3) the VRH-group receives a digital sedation in contrary to the control group who will not use the VRH headset.

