11.4 ANALYSIS

First descriptive analysis will be performed. Qualitative data will be described by frequency and percentage. Quantitative data will be described by mean, standard deviation, median, minimum, and maximum numbers.

Regarding the primary outcome, NRS pain score before and after the intervention will be compared using paired t-test or Mann-Whitney test, depending of data distribution. 95% confidence intervals will be provided.

Regarding secondary outcomes, chi-squared tests will be used to compare frequencies and rates between groups. In case of small cell sizes, we will alternatively use the Fisher's exact test. T-Test or Mann-Whitney test will be used to determine if there is a significant difference between means of the two groups. T-Test or Mann-Whitney test will be also used for all continuous data normally distributed or not such as NRS, Likert scale and physiologic data. Repeated measurements such as Anxiety and Nausea will be handled with appropriate techniques such as paired tests.

Safety variables include the incidence of Serious Adverse Events (SAEs), discomfort and the quality of immediate and distant labor pain analgesia. These data will be tabulated by treatment groups and overall, in contingency table for percentages or in descriptive univariate analyzes for continuous variables.

The Intent-to-Treat (ITT) population will be used for all efficacy and safety analyzes unless otherwise specified. This ITT analysis will include all randomized patients, according to their allocation group.

The Per-Protocol (PP) population will be used to validate the effectiveness of the studied intervention, as specified by the primary outcome. This PP analysis will include all patients in the ITT population who do not have a major violation of the protocol. The list of major violations includes at least:

- Non-administered medication
- Failure to meet an inclusion or exclusion criterion

Patients identified as having major violations will be screened to determine their final exclusion from the PP population, prior to the freezing of the database.

12.QUALITY CONTROL AND QUALITY ASSURANCE

Increased adherence to the protocol is acquired by multiple information sessions about the study for the midwives. Furthermore, a reminder poster will be displayed in their office. Adherence to the protocol by the participants will be monitored daily by a non-blinded investigator (LP) by looking at the daily reports of the study.

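### The 0-8 CPOT total is not comparable between arms, because its facial item is rated with goggles on in the VRH arm only and no rule covers a hidden face

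*Combined protocol and SAP*

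**What the plan says.** The synopsis lists the endpoint as "Evaluation of comfort during intervention with the CPOT scale (Critical care Patient Observation Tool 0 to 8) and heart rate", under the objective "To compare patient experience in both arms". Section 5.2 places the assessment at T2, during the intervention, and gives the content of the score: "Facial expression, body movements, muscle tension and vocalization together make a score of 0 to 8".

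The synopsis entry on the medical device says that the kit "consists of an audio headset, virtual reality goggles, a mobile phone" and further components. Section 6 states that between T1 and T3 "the VRH-group receives a digital sedation in contrary to the control group who will not use the VRH headset". Section 11.3 says that the investigators are not blinded, because they can see who is using the headset while they take the measurements.

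Section 11.4 does not name CPOT. Its general rule for secondary outcomes is: "T-Test or Mann-Whitney test will be used to determine if there is a significant difference between means of the two groups".

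Sections 5.2, 9 and 11.4 do not say how facial expression is scored under goggles, whether the total is prorated, or whether the item may be left out. The data collection form (Questionnaire 3) is not reproduced in the document, so a rule printed only there could not be checked.

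**The concern.** A between-arm comparison of a rating scale assumes that each item can be observed equally well in both arms. Here one of four items depends on seeing the face, and the face is partly behind a device in one arm only. Randomisation does not remove this, because the difference arises from how the outcome is measured and not from who is in each arm.

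A grimace that cannot be seen is most naturally scored as absent. That lowers the total, which reads as more comfort, in the VRH arm. A rater who instead infers the hidden part of the face does so knowing the allocation.

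CPOT is the only observer-rated comfort scale at T2. If it comes out lower under VRH, the trial could not tell how much of the difference is comfort and how much is the goggles.

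**Working it through.** **Inputs from the documents.** Four items including facial expression, total 0-8 (5.2). T2 falls during the session (5.2, 9). The headset is worn in one arm only (6). Raters are unblinded (11.3). 17 evaluable patients per arm, two-sided 5% test (11.1).

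**Assumptions.** Items are equally weighted, so the facial item carries 8/4 = 2 points, or 25% of the scale. The documents give no SD for CPOT; I take 1 to 2.5, with 1.5 to 2 as the central range. The size of the artefact is also not given, so it is varied.

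**The plan's own figure.** Section 11.1 sizes the trial on NRS pain (difference 2, SD 2). With n = 17 per arm the standard error is 2·√(2/17) = 0.686 and the noncentrality is 2/0.686 = 2.915. The noncentral t with 32 df gives 80.7% power; n = 16 gives 78.1%. So 17 per arm reproduces, and 17/0.9 = 18.9, rounded up to 19 per arm, gives 38 in total. CPOT played no part in the sizing.

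**Chance of a significant CPOT difference when there is none.** Let b be the mean number of points hidden by the goggles and s the SD. The noncentrality is b/(s·√(2/n)), and the rejection probability is P(|t| > 2.037) under the noncentral t with 2n − 2 = 32 df. For example, b = 0.5 and s = 2 give 0.5/0.686 = 0.729 and a probability of 10.9%.

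| Mean artefact (points) | SD 1 | SD 1.5 | SD 2 | SD 2.5 |
|---|---|---|---|---|
| 0 | 5.0% | 5.0% | 5.0% | 5.0% |
| 0.25 | 10.9% | 7.6% | 6.4% | 5.9% |
| 0.5 | 29.3% | 15.6% | 10.9% | 8.7% |
| 1.0 | 80.7% | 47.0% | 29.3% | 20.5% |

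An artefact of 0.25 corresponds to one VRH patient in four losing a point, and 0.5 to one in two.

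**Item-level check.** I simulated 3,000 trials of 17 per arm with no true effect. Each had four items scored 0, 1 or 2 with probabilities 0.3, 0.4 and 0.3, and a latent correlation of 0.4. These inputs are assumptions; they give a mean facial score of 0.4 + 2 × 0.3 = 1.0 and an SD of the total of about 2.15.

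| Facial item in the VRH arm | Mean artefact | Significant on 0-8 | Significant on three items, 0-6 |
|---|---|---|---|
| Not masked | 0 | 5.0% | 5.2% |
| One category lower in half of patients | 0.34 | 7.8% | 5.7% |
| Scored 0 in half of patients | 0.50 | 10.2% | 4.9% |
| One category lower in all patients | 0.70 | 16.1% | 5.4% |
| Scored 0 in all patients | 1.0 | 30.2% | 5.7% |

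The three-item subtotal holds its level in every scenario, because it does not use the masked item.

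**The case against.** **The between-arm test is inferred.** Section 11.4 does not name CPOT. Section 5.2 justifies the scale by the difficulty of talking with a patient during VR, and the section 9 schedule labels it a VR comfort scale and places it during AQUA. The same synopsis objective also holds willingness items about VRH, which controls have not experienced, so being listed there does not prove a two-arm test. If CPOT is recorded in the VRH arm only, there is no comparison to bias. This stands as an ambiguity that the plan must resolve. It does not settle the matter: the schedule words T1 and T3 in terms of AQUA as well, yet the primary comparison between arms needs both time points in controls.

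**The direction is not shown.** A reader might infer that the plan certainly biases comfort towards VRH. The documents do not support that. They neither say that a hidden feature is scored 0 nor describe how much of the face is covered. Section 14.1 credits the midwives with a year of VRH experience, and section 5.2 says that staff already watch similar signs during VR sedation, so raters may use what remains visible. This stands: an advantage for VRH is the plausible direction, not an established one.

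**The size is assumed.** With no true effect, goggles cannot hide more than the facial score that is there. A 1.0-point artefact therefore needs a mean facial score of at least 1.0 out of 2, and at exactly 1.0 every VRH patient must be scored 0. The face is unlikely to be that fully hidden. The 47% figure should carry no weight.

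**A 0-6 subtotal is ad hoc.** True, and the documents offer nothing on its validity. But the 0-8 total has lost its common meaning across the arms, which is the greater problem for a comparison.

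**Conclusion.** The point holds as a threat to one secondary outcome. As written, a between-arm difference in the 0-8 total could partly be a device artefact, most plausibly favouring VRH. With SD 1.5 to 2 and 17 per arm, the false-positive rate is about 6-8% for a 0.25-point artefact and 11-16% for 0.5; 29-47% at 1.0 point is an extreme case. All of these rest on an assumed SD, equal item weights and an assumed amount hidden, and they apply only if CPOT is in fact compared between arms.

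Two wider readings should be resisted. CPOT is not the only comfort-related measure during the session: the synopsis pairs it with heart rate, and section 5.2 also lists an anxiety NRS at T2, although the section 9 schedule omits anxiety. Nor does this reach the main result: the primary endpoint is NRS pain at T3 minus T1 (5.1), and it and the sample size are untouched.

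**What to change.** In 5.2, 11.4 and Questionnaire 3:

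- State whether controls are rated on CPOT and, if so, when T2 falls for them.
- Make any between-arm CPOT comparison on the sum of body movements, muscle tension and vocalization (0-6).
- Record a covered facial item as *not assessable*, not as 0.
- Report the facial item and the 0-8 total descriptively only.
- If CPOT is intended for the VRH arm alone, say so and drop the between-arm comparison.

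This costs a few lines of text and one response option on the form, with no extra patients or visits. The 0-6 subtotal departs from the standard scale and cannot be set against published 0-8 values. It removes only the goggle artefact: the other three items are still rated unblinded, and the report should name that as a limitation.

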9. SCHEDULE OF ASSESSMENTS AND PROCEDURES

RCT T	TO	T1	T2	T3	T4	T5	T6
Delivery Phase	Prenat consult	Active Labor (study threshold) Day 0	Labor	Labor	Labor	End of Delivery	Day 1
		Before the Start AQUA	During AQUA	End AQUA	T3+30 min		
Screening/ ICF	X						
Refusal questionnaire	X						
Patient Questionnaires & Observation							
NRS pain		X		X	X		
Nausea		X		X	X		
Likert satisfaction							X
CPOT (VR comfort scale)			X				
Willingness to repeat (intervention)							X
Recommend (intervention)							X
Practitioner questionnaire							
Monitored contractions (on the CTG during intervention)				X			
Satisfaction midwife						X	
Quality of the therapeutic relationship						X	
Objective criteria							
Vital signs (Saturation)		X	X	X	X		
Medication received							X
Epidural				X	X		
Progression of labor							X
(Serious) adverse events		X	X	X	X	X	
Stop of digital sedation session				X			

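### Anxiety is planned and named for analysis but missing from the schedule and the synopsis endpoints, and its T2 self-report falls when VRH patients cannot be questioned

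*Combined protocol and SAP*

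**What the plan says.** Section 5.2 (Secondary outcomes) introduces anxiety directly after nausea, which is rated at T1, T3 and T4: "Anxiety is evaluated with the NRS at the same time. (T1, T2, T3". The same section places the observer-rated CPOT in the session, "During the intervention the comfort of the patient is evaluated. (T2", and explains why an observer scale is needed: "during the VR experience we cannot communicate with the patient, which is similar as in sedated patients". It also plans patient satisfaction at T3 and T6.

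Section 11.4 (Analysis) names anxiety once: "Repeated measurements such as Anxiety and Nausea will be handled with appropriate techniques such as paired tests". Its general text on secondary outcomes also provides a t-test or Mann-Whitney test between the two groups, and applies these tests to continuous data, including NRS scores.

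In section 9 the block headed "Patient Questionnaires & Observation" has rows for pain NRS, nausea, satisfaction, CPOT, willingness to repeat and recommendation. It has none for anxiety. The row "Likert satisfaction" carries a single tick, at T6.

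The synopsis lists no anxiety endpoint. Anxiety appears there only in descriptions of the device, for example that the module is "specifically designed for the management of pain and anxiety during labor".

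**The concern.** The schedule is the table that ward staff work from. An outcome that the analysis section expects but the schedule does not collect may have no data at the end, and a rating taken in labor cannot be recovered afterwards. Anxiety also matters for interpretation, because it is one of the two things the module is described as managing.

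Staff who follow section 5.2 literally meet a different problem. At T2 a VRH patient is under the headset and, on the protocol's own account, cannot be spoken to, whereas a control patient can. The T2 rating is then missing according to arm, or it is obtained by breaking into the session being tested.

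With anxiety present in two places and absent from two others, a reader of the final report could not tell whether an anxiety result, or its absence, was prespecified.

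**Working it through.** The plan gives no figure for anxiety, so the check is a comparison of the sections.

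| Item | Section 5 | Section 9 | Synopsis endpoints | Named in 11.4 |
|---|---|---|---|---|
| Pain NRS | T1 and T3 (5.1), T4 (5.2) | T1, T3, T4 | yes | yes |
| Nausea | T1, T3, T4 | T1, T3, T4 | yes | yes |
| Anxiety NRS | T1, T2, T3 | no row | no | yes |
| CPOT | T2 | T2 | yes | no |
| Patient satisfaction | T3, T6 | T6 only | yes, no time given | Likert scale, in general terms |

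1. **Missing row.** Pain, nausea and CPOT agree between section 5 and section 9. Anxiety is the only item in this table with no row at all. The other rows survived the PDF reading and there is no stray anxiety label, so loss in extraction is unlikely.

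2. **T2 against the communication statement.** Section 9 defines T2 as during AQUA. Its ticks at T2 are CPOT, vital signs and adverse events, none of which is a scheduled patient self-rating. The synopsis likewise describes patient reports before the intervention, after it and up to discharge, not during it. An anxiety NRS is a self-report, so the T2 entry in section 5.2 conflicts with all of this.

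3. **Consequence by arm at T2.** With 19 women randomized to each arm (section 11.1), ratings obtainable without interruption are at most 19 of 19 in the control arm and 0 of 19 in the VRH arm. No between-arm comparison at T2 is then possible. The control figure is an upper limit, because T2 is defined by a session that controls do not have.

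4. **Timing phrase against bracket.** The preceding sentence rates nausea at T1, T3 and T4. If anxiety is taken with nausea, its times are T1, T3 and T4. The bracket says T1, T2 and T3. The two readings share T1 and T3 and differ on T2 and T4. T2 may be a slip, but the documents do not settle it.

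5. **If section 9 alone is followed.** Provided Questionnaire 3 has no anxiety field, 0 of 38 women would have anxiety data. The same condition applies to satisfaction at T3.

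6. **What a paired test answers.** Within an arm it tests whether the mean of T3 minus T1 is zero. The treatment question is whether that change, or the T3 value given T1, differs between arms. The sentence naming anxiety gives only the first as its example.

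7. **Sample size.** For a difference of 2, SD 2, 80% power and two-sided 5% alpha, the normal approximation is 2 × (1.960 + 0.842)² × (2/2)² = 15.7, so 16 per arm. The t-based calculation gives 16.7, so 17, with 80.7% power at 17. Then 17 / (1 − 0.10) = 18.9, so 19 per arm and 38 in total. This reproduces section 11.1. It rests on pain only, so the anxiety question does not change it.

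**The case against.** The strongest reply is that this is a wording slip in a secondary outcome with little practical consequence. Several parts of that reply stand.

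- **Between-arm testing.** A reader might infer that no between-arm anxiety test is planned, because the sentence naming anxiety mentions only paired tests. The documents do not support that. The general text of section 11.4 already allows a t-test or Mann-Whitney test between groups for NRS data, and the paired tests are given only as an example. What remains is that the anxiety comparison is not stated clearly.
- **Certain loss of data.** A reader might infer that all 38 women will lack anxiety data. Section 14.1 says that Questionnaire 3 is used to record all the outcomes described before it, which would cover section 5.2. The form is not in the documents, so the loss is conditional. A field on the form would prevent it but would not reconcile the sections.
- **Disturbing the primary rating.** A reader might infer that a T2 question would disturb the session immediately before the primary T3 pain rating. The documents give neither the session length nor the moment of T2 within it. Only the interruption itself can be claimed.
- **Satisfaction at T3.** This depends on the position of one tick in a table read from PDF. In the same table, progression of labor and medication appear only at T6, whereas section 5.2 gives T5 for the first and T3 and T5 for the second. Either columns moved in reading or the schedule departs from section 5.2 more widely. The missing satisfaction tick is therefore less certain than the missing anxiety row.
- **T4.** An anxiety rating at T4 rests only on the ambiguous timing phrase.

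The reply does not remove the contradiction itself: an outcome named for analysis has no place in the schedule or the synopsis endpoints, and one of its three stated times is unworkable in one arm.

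**Conclusion.** The inconsistency is real and should be corrected before recruitment or, if recruitment has begun, as soon as possible. It affects one secondary outcome, and probably the T3 reading of another.

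At T2, a self-reported anxiety score would be available for at most 19 controls and for no VRH patient without interruption. This takes section 5.2's statement about communication at face value. Complete loss of anxiety data follows only if staff work from section 9 alone and Questionnaire 3 has no anxiety field; neither can be checked here. The satisfaction point assumes that the table columns were read correctly.

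The primary endpoint (T3 minus T1 pain) and the total of 38 patients are unaffected.

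**What to change.** - Reconcile the synopsis endpoints, section 5.2, section 9 and section 11.4, and check Questionnaire 3 against the result.
- Delete the T2 anxiety self-report from section 5.2. The observer-rated CPOT stays at T2.
- Add an anxiety NRS row to section 9 at T1 and T3 at least. Add T4 only if the sponsor confirms that anxiety is meant to be taken at the nausea time points, and make section 5.2 match.
- List anxiety among the secondary endpoints in the synopsis.
- Tick patient satisfaction at T3 in section 9. In the same edit, compare the remaining rows with section 5.2, in particular progression of labor and medication.
- State in section 11.4 that anxiety is compared between arms at T3, preferably adjusted for T1, for example by regressing the T3 score on arm and T1 score. Within-arm paired tests can remain as description.

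The cost is a set of table and wording edits, and one 0 to 10 question at time points that staff already attend. No extra patients are needed.
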